In addition to associations between DHA supplementation and prenatal stress, we observed significantly higher birth weights among neonates born to women receiving DHA compared to placebo controlling for gestational age (3,174 grams versus 2,889 grams, p = .018) and greater likelihood of having a 1-minute Apgar score of 9 (odds ratio = 5.99 [95% Cl = 1.25 - 28.75], p = .025, controlling for birth weight and gestational age). Finally, 13% of neonates of mother receiving DHA supplementation were born prior to 37 weeks, compared to 22% of mothers received placebo; a difference that did not reach the level of statistical significance in the pilot study, but is clinically meaningful.

In summary, the data from our preliminary study are compelling in terms of the potential impact on health disparities in maternal and infant health, a significant public health problem that is poorly understood. We now seek to expand on these preliminary findings by conducting a more rigorous assessment of prenatal DHA supplementation on maternal and infant health by increasing the number of participants to 162, beginning supplementation earlier in pregnancy, adding additional measures of maternal health and stress response during pregnancy, increasing the frequency of assessment, assessing DHA levels in red blood cells at each visit, and including multiple postnatal assessments of infant neurodevelopment. The proposed study offers an opportunity for replication and to test the impact of supplementation on infant functioning and, if effects are observed, whether they are mediated by changes in prenatal stress.

APPROACH

Participants

One hundred-sixty-eight pregnant, African American, women will be recruited from the University of Chicago obstetric clinic. Inclusion criteria will include: age between 18 and 34 years, household receipt of public assistance (e.g., Medicaid insurance) due to low-income, and low levels of DHA consumption as defined as less than two fish servings per week. Exclusion criteria are reports of known medical complications, regular use of steroid medications, alcohol, cigarettes, or illegal substances (by maternal report), use of blood thinners or anti-coagulants, use of psychotropic medications, BMI >40, and allergy to iodine and/or soy. Participants may be excluded if medical complications arise after enrollment. Neonates with significant medical complications will be maintained in the study.

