There are two reasons for our focus on African American women. First, as described above, African American women are disproportionately represented among families living in inner-city poverty and have the highest rates of suboptimal birth outcomes in the U.S. (Giscombé & Lobel, 2005). Second, there are racial differences in cortisol reactivity to

stress and pregnancy (De Santis et al., 2007; Glynn et al., 2007; Wilcox et al., 2005) and in the genes regulating cortisol (Baerwald et al., 1999). Given the scope of the proposed study and the potential to generate data that can be translated into reductions in health disparities, we chose to study African Americans only, but acknowledge that it will be important to test racial and ethnic differences in maternal and infant response to DHA supplementation during pregnancy.

Women will be randomly assigned to receive the omega-3 nutritional supplement (n = 112) or a corn and soybean oil placebo (n = 56) beginning at enrollment and up through the end of pregnancy. In the proposed design we allocate the number of participants to groups to optimize power to test the hypotheses. We expect greater variability in the independent measure (i.e. DHA level) and dependent measures (e.g., stress reactivity) in participants in the experimental group than those in the control group given anticipated differences in uptake and metabolism. Thus, we plan to enroll a higher number of participants in the experimental group than in the control group to adequately capture that variability (Cox, 1958). Participants and investigators will be blinded to the group to which they have been assigned. Treating clinicians will identify demographically eligible participants who will be contacted by research staff for further screening. Participants who meet the inclusion and exclusion criteria will then be scheduled for the baseline visit.

Participants will be reimbursed on an accelerated schedule with \$100 for their first visit and an increase in payments by \$25 for each subsequent visit, ending with a \$250 payment for the last post-partum visit. Participants will receive incentives in between visits including water bottles, tote bags, newborn t-shirts, etc. They also will be reimbursed with \$10 to cover travel costs for each visit.

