Response to a controlled stressor including cortisol, blood pressure, and heart rate will be better modulated among women receiving DHA supplementation than among women who do not, as demonstrated by a lower peak response and more rapid recovery to baseline. Differences in stress reactivity (i.e., cortisol levels, blood pressure, and heart rate) will be tested using two complementary approaches. First, we will use rmANOVA with supplement group as the between-subjects factor and timing of measurement (e.g. 20 minutes and 5 minutes pre-TSST, and 20, 40, and 50 minutes post-TSST for cortisol) as the within-subjects factor for each of the 4 prenatal visits separately. The interaction between group and time will be tested. For further interrogation of these changes, a random intercept, random slope mixed-effects model will be fit and results compared to the rmANOVA results. Second, the area under the curve (AUC) will be calculated for each participant at

each visit. Since primary interest is in assessment of changes over time, the AUC_I (area under the curve with respect to increase) will be used (Pruessner et al., 2003). Differences in these AUCs will be tested using rmANOVA with supplement group as the between-subjects factor and visit as the within-subjects factor. The interaction between group and visit will also be included to explore whether the magnitude of the difference between the groups is affected by the length of DHA supplementation. A Greenhouse-Geisser sphericity adjustment will be employed in both rmANOVA analyses. For further exploration of the patterns over time, a cluster analysis using the AUCs at each visit will be performed, and the association between the "change groups" formed from this cluster analysis and supplement group will be determined using a chi-square or Fisher's exact test. Log-transformed cortisol values will be used if appropriate. Also, time of collection and prenatal depression and anxiety will be controlled for in these analyses if needed.

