Power Calculations for Hypothesis 1. In this study with 108 participants in the supplement group and 54 in the placebo group, there will be >90% power to detect a difference in stress levels, at any particular visit, of the same magnitude as that observed in our preliminary study at 30 weeks (27.5+/-3.4 vs. 29.3+/-3.1), using a two-sided test at the 0.05 significance level. Additionally, with 162 participants, there will be 80% power to detect a correlation of 0.22 between changes in DHA levels in the blood versus changes in perceived stress. For the cortisol response to the TSST, there will be >95% power to detect a difference in AUCs at a given visit of the same magnitude as that found in our preliminary study at 30 weeks (-4.5+/-3.9 vs. -8.1+/-6.1; negative values indicating net decreases rather than increases), using a two-sided test at the 0.05 significance level.

Hypothesis 2. DHA supplementation during pregnancy will improve infant birth and developmental outcomes among African American women living in urban poverty.

Infants of mothers who receive DHA supplementation will have longer gestations, higher birth weights, more optimal neurodevelopmental outcomes as measured by the NBAS and Bayley Scales of Infant Development, and more optimal maternal reports of temperament in comparison to infants whose mothers did not receive DHA supplementation. We will use ANOVA (e.g. birth weight) or rmANOVA (e.g. NBAS) to test for significant differences between treatment groups. For categorical infant outcomes, such as pre-term birth or low Apgar scores, logistic regression will be employed. We will also test the association between level of DHA in blood at the last prenatal visit and/or change in DHA levels from baseline and infant outcomes using linear (e.g. birth weight or change in NBAS) or logistic (e.g. pre-term birth) regression.

Transformations of the continuous dependent measures will be performed to stabilize the variance across groups if needed.

Infants of mothers who received DHA supplements will demonstrate more modulated cortisol response to the NBAS and still-face paradigm, with a lower peak response and a steeper slope from peak to recovery, in comparison to infants whose mothers did not receive DHA supplementation. Analyses will be performed as described for Hypothesis 1.

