 Y_i is an outcome for infant i, g is a link function (e.g. logistic or identity), M_i is a maternal stress measure at the final prenatal visit for the mother of infant i, T_i is treatment group (e.g. 0=placebo vs. 1=active; average DHA level in the blood across prenatal visits), and Z_i is a vector of additional covariates such as infant gender, mothers' postpartum stress, depression, or anxiety. The change in ω due to adding maternal stress to the model provides an estimate of the proportion of the treatment effect due to this factor; if ω is still significant but the magnitude is reduced, this would provide evidence for partial mediation. For infant outcomes collected at multiple visits, the initial approach will be to use data from the last visit, but longitudinal approaches may be considered depending on the results from the initial analyses. To provide greater power for detecting such effects, bootstrapped confidence intervals will be examined. Since multiple measures of maternal stress will be collected, the model may be extended to permit multiple mediators.

Power Calculations for Hypothesis 3. Based on simulation results presented in Fritz et al. and the SAS program provided at http://ripl.faculty.asu.edu/wp-content/uploads/2013/02/baronkenny3.txt, 162 subjects will provide sufficient power (>80%) to detect the following effects based on Cohen's criteria. As shown in Figure 6 and Table 2, the study with 162 subjects will be sufficiently powered (>80%) to detect medium effects for the α and β paths and small effects for the direct effect (scenario 1), or small-medium effects for the α and β paths and medium effects for the direct effect (scenario 2), which is plausible based on the effects found in the preliminary study.

Table 2: Overview of power for mediation hypothesis

	α path	β path	Direct effect	
scenario 1	medium	medium	small	
scenario 2	small-medium	small-medium	medium	

Missing data. Missing data is not expected to be a major issue based on retention rates from the preliminary study. The last observation carried forward (LOCF) approach for missing data will be employed. Sensitivity analyses using complete-cases only will also be performed and the results using the two approaches compared. Related to this, treatment non-compliers will be included in the primary analysis based on the intent-to-treat (ITT) principle.

Timeline for participant visits

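### Relating birth outcomes to DHA at the last prenatal visit lets early delivery partly set the recorded exposure, which can create a spurious protective association

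*Combined protocol and SAP*

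**What the plan says.** Under Hypothesis 2, the main tests compare the randomised groups by ANOVA, repeated-measures ANOVA or logistic regression. The plan then adds tests of "the association between level of DHA in blood at the last prenatal visit and/or change in DHA levels from baseline and infant outcomes", using linear (for outcomes such as birth weight) "or logistic (e.g. pre-term birth) regression". Gestational length is also a Hypothesis 2 outcome.

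The other pieces are spread over the document:

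- Blood for DHA is drawn at every prenatal visit: the closing summary of the preliminary-data section plans on "assessing DHA levels in red blood cells at each visit". The Hypothesis 1 analysis text counts the visits ("for each of the 4 prenatal visits separately"), and Table 1 places the last two at 24-30 and 34-36 weeks.
- The Participants section has supplement taken "beginning at enrollment and up through the end of pregnancy".
- The Missing data paragraph states: "The last observation carried forward (LOCF) approach for missing data will be employed". A complete-case sensitivity analysis will be compared with it.
- The only adjustment for stage of pregnancy is conditional and concerns cortisol (Methods, maternal stress response).

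For these DHA regressions the plan fixes no sampling week and no rule for women who deliver before the last draw. It does not adjust for gestational age at sampling or for weeks on supplement.

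**The concern.** Preterm birth means delivery before 37 weeks, and the last draw is at 34-36 weeks, so some of the women who have the outcome will have delivered before that draw. If the last prenatal visit means the last one attended, their DHA value comes from 24-30 weeks or earlier. If it means the scheduled 34-36 week visit, carrying forward puts the same earlier value in that slot. Either way, in the active arm the value follows fewer weeks of supplement than the values of women who reached the last draw. Change from baseline to the last visit has the same defect.

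If DHA is still rising between those visits, early delivery itself lowers the recorded exposure. Low DHA then goes with preterm birth, low birth weight and short gestation even when DHA has no effect. This is the direction the trial hypothesises, so a reader could take the artefact for a relation between achieved DHA and outcome.

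**Working it through.** **1. The nearest stated figure.** The plan gives no power or effect size for the DHA-level regression. The closest figure is about 90% power for the between-group birth weight difference (3174 ± 480 vs 2889 ± 549 g; 108 vs 54; two-sided 0.05).

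- SE = √(480²/108 + 549²/54) = √(2133.3 + 5581.5) = 87.8 g
- 285/87.8 = 3.245, and Φ(3.245 − 1.96) = 0.90

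The figure reproduces. It belongs to the randomised comparison, which this point does not touch.

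**2. How many women are affected.** Pilot preterm rates were 13% (active) and 22% (placebo). Weighted 2:1 this is (2 × 13 + 22)/3 = 16%, and 0.16 × 162 = 25.9, so about 26 women. Not all of them miss the last draw. Assuming that 20-45% of preterm births fall before 34 weeks and that the last visit is spread over 34 to 36 or 37 weeks, about 8 to 16 women do (5-10% of 162).

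**3. Simulation with no true effect.** From the documents: 108/54 women, 16% preterm (set equal in both arms), visits in the Table 1 windows, two-sided 0.05. Assumed: first visit at 8-15 weeks; birth weight slope 150 g per week; gestation independent of DHA; no adjustment for arm, since the plan states none. Active-arm DHA rises as plateau × (1 − exp(−weeks on supplement/τ)), in units of the between-woman SD. A correlation test stands in for the linear and logistic models. There were 2,000 replicates per scenario (Monte Carlo SE near 5%: √(0.05 × 0.95/2000) = 0.5 points) and 4,000 for the last two rows. Ranges cover the early-birth scenarios of step 2.

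| DHA value used | Rise | Mean r with preterm | False positives, preterm | False positives, birth weight |
|---|---|---|---|---|
| Last available | τ = 4 weeks, plateau 2 SD | −0.005 to −0.013 | 4.4-4.8% | 4.4-5.4% |
| Last available | τ = 10, plateau 2 | −0.019 to −0.040 | 6.0-6.8% | 5.4-6.0% |
| Last available | τ = 20, plateau 4 | −0.034 to −0.073 | 5.6-14.3% | 5.5-10.7% |
| Last available | τ = 20, plateau 6 | −0.035 to −0.078 | 6.0-14.2% | 5.9-11.2% |
| 24-30 week visit, still pregnant | τ = 20, plateau 4 or 6 | −0.002 to 0.000 | 4.6-4.7% | 4.6-4.8% |
| Complete cases at 34-36 weeks | τ = 20, plateau 4 | −0.001 | 5.0% | 5.5% |

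The complete-case row excludes about 14 women, all of whom delivered before their last draw.

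**4. Linear rise without a plateau.** With 0.05 to 0.15 baseline SD per week, 16% preterm and about 14 women missing the last draw, the preterm false-positive rate was 9-19%. Other settings for the preterm rate and the share of very early births gave 6-21%. In runs with about 15 women missing the draw, change from baseline did somewhat worse than level (14-25% against 11-21%), and the 24-30 week sample stayed at 5-6%.

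**The case against.** Four objections deserve an answer.

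**The size depends on kinetics that nobody has stated.** This stands. If red-cell DHA levels off within a few weeks, the earlier and later samples hold nearly the same value and there is no inflation. Even at 20%, four null trials in five would show nothing significant. A reader might infer that the analysis would show low DHA predicting preterm birth whatever the truth. The documents support only that it can.

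**The analysis is an addition.** This also stands. Hypothesis 2 is tested by randomised comparison, and those tests do not use the DHA value. A reader might infer that the trial's birth-outcome result is biased, or that this regression is the evidence the trial means to rely on. The documents say neither.

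**The complete-case analysis already covers it.** Partly. Its error rate was close to nominal, and a divergence from the carried-forward analysis would be a warning. But it restores the timing by removing the earliest deliveries, which are the most severe outcomes, and it is a sensitivity analysis only.

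**Hypothesis 3 has the same fault.** This is tempting, because the mediator "is a maternal stress measure at the final prenatal visit". But the mediator is a stress measure, not DHA. The mechanism shown here is DHA accumulating with weeks of supplement, and it does not carry over automatically. No calculation here tests it, and for cortisol the plan already has a conditional control for stage of pregnancy. Moving the mediator earlier would also have a price: in the pilot, the group differences in perceived stress and cortisol were absent at 24 weeks and appeared at 30.

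**Conclusion.** The point holds for the secondary Hypothesis 2 regressions of preterm birth, birth weight and gestational age on DHA level at the last prenatal visit or change from baseline. The direction follows from the plan's own visit schedule, outcome definition and carry-forward rule, provided that DHA is still rising between the last two draws. Nothing in the plan removes it.

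The size is uncertain. For DHA level and preterm birth, the false-positive rate runs from about 5% to about 20%. It rests on the assumed shape of the DHA rise and on the assumed share of preterm births that precede the last draw, and the upper figure is not a bound. The shorter-supplementation mechanism acts in the active arm only. Gestational age was not simulated as an outcome; it is included because the reasoning is the same. Because the remedy is cheap and the artefact favours the hypothesis, the plan should be changed before unblinding.

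**What to change.** Amend the Hypothesis 2 and Missing data text as follows:

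- For birth outcomes, define DHA exposure (level, and change from baseline) at the 24-30 week visit, among women still pregnant at that visit.
- Carry no DHA value forward past delivery.
- Keep the 34-36 week DHA value for postnatal outcomes.
- Leave the Hypothesis 3 mediator where it is; this evidence does not justify moving it.

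The blood is already scheduled, so the change costs only plan wording. The downside is small: the regression reflects a shorter period of supplementation, and its conclusion applies to women still pregnant at the 24-30 week visit. If the sponsor wants to use the later samples for birth outcomes, DHA could instead be modelled by gestational age and time on supplement, which needs more assumptions.

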Measure	Variables		16-20 wks	24-30 wks	34-36 wks	1 month	4 months	9 months
Maternal Psychosocial Stress								
Perceived stress	Perceived stress Total score from PSS		1	>	>	>	>	1
Life events	Life events Total score from DLC		1	1	1	1	1	1
Depressed mood		1	1	1	1	1	1	1
Anxiety Total score from STAI		/	1	1	1	1	/	1
Maternal Stress Response								
Reactivity to TSST	Cortisol; HR, BP	>	1	>	>			
DHA Levels								
Blood draw	DHA levels in red blood cells	>	1	1	1			
Maternal Inflammatory Markers								
Blood draw	CRP; IL-6; TNF-α	>	1	>	>			
Infant Outcomes								
Birth	Birth weight, gestational age, Apgar, meconium					1		
Neurodevelopmental functioning	NBAS, BSID					1	1	1
Stress reactivity	Cortisol response to NBAS, FFSF					>	>	1
Temperament	IBQ; IBQ-R – short form						1	1

Table 1. Overview of main study variables

Hypotheses and Analyses

Hypothesis 1. DHA supplementation will improve maternal health during pregnancy among African American women living in urban poverty. Women who receive DHA supplementation will report lower levels of self-reported perceived stress over time, despite a lack of change in exposure to environmental stressors. Inflammatory markers including C-reactive protein (CRP), IL-6, TNF-α will be lower among women receiving DHA supplementation compared to placebo. To test for significant differences in perceived stress and inflammatory marker levels we will use repeated measures ANOVA (rmANOVA) with supplement group as the between-subjects factor and visit as a within-subjects factor. The interaction between group and time will be of particular interest. A Greenhouse-Geisser sphericity adjustment (Geisser & Greenhouse, 1958) will be employed. If any of the dependent measures exhibit a non-normal distribution (e.g. CRP), then a suitable data transformation will be used. Changes over time in prenatal levels of depression and anxiety will also be assessed using rmANOVA. Scatter plots and box plots of the data will be used to further explore these relationships. Plots of the data also will be examined to detect nonlinear time effects in addition to using orthogonal polynomial contrasts to formally test for quadratic and cubic effects. The association between change in DHA levels in the blood from baseline to the last prenatal visit and change in perceived stress will be examined using linear regression models.

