Infant gender, mothers' postpartum stress, depression, and anxiety levels will be compared between those received DHA supplements during pregnancy and those who did not using ANOVA. If significant differences are found, then these factors will also be controlled for in the analyses. If time of collection is associated with cortisol values, then this will also be controlled for in the analyses. However, since a circadian rhythm is not firmly established prior to the age of 6 months, we do not expect to have to control for time of day at 1 and 4 months.

Power Calculations for Hypothesis 2. Based on published data on maternal report of difficult temperament in infants using the ICQ (Keenan et al., 1998), the estimated SD for the ICQ in the proposed study is 7.8. With 108 participants in the supplement group and 54 in the placebo group, there will be 80% power to detect a difference in the ICQ of 3.7 between the two groups at a given visit, using a two-sided test at the 0.05 significance level.

The SD for 30–minute post-test cortisol levels in response to the FFSF paradigm was reported as 0.4 μ g/dL (Hayley & Stansbury, 2003). If we assume a similar amount of variability in peak responses to the FFSF, with 108 participants in the supplement group and 54 in the placebo group, there will be 80% power to detect a difference of 0.19 μ g/dL between the two groups, using a two-sided test at the 0.05 significance level.

[figure not shown]
In addition, there will be approximately 90% power to detect a difference in birth weights of the same magnitude as that observed in our preliminary study (3174+/-480 vs. 2889+/-549 g), using a two-sided test at the 0.05 significance level.

Hypothesis 3. The association between DHA supplementation during pregnancy and infant outcomes will be partially mediated by reductions in maternal perceived stress, stress reactivity during pregnancy.

Mediation will be tested using the Baron and Kenny approach (Baron & Kenny, 1986) with the following general model:

$$g(E(Y_i)) = \alpha + \beta M_i + \omega T_i + \lambda Z_i$$

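### Hypothesis 2 lets a significance test on mothers' postpartum mood decide whether infant outcomes are adjusted for it, so the supplement effect could be biased if supplementation itself alters that mood

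*Combined protocol and SAP*

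**What the plan says.** All references are to the combined protocol and SAP.

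- **The test (Hypothesis 2).** Infant gender is compared between arms and, in the same sentence, mothers' "postpartum stress, depression, and anxiety levels will be compared between those received DHA supplements during pregnancy and those who did not using ANOVA". The significance level and the postpartum visit to be used are not given.
- **The consequence (Hypothesis 2).** "If significant differences are found, then these factors will also be controlled for in the analyses".
- **Timing (Table 1).** The maternal measures, such as the row "Perceived stress Total score from PSS", are scheduled at 1, 4 and 9 months as well as prenatally. Supplementation runs only to the end of pregnancy (Participants).
- **Reach.** The text just before the rule concerns infant cortisol and ends "Analyses will be performed as described for Hypothesis 1". The section as a whole also covers "longer gestations, higher birth weights, more optimal neurodevelopmental outcomes as measured by the NBAS and Bayley Scales of Infant Development". Which of these the rule applies to is not stated.
- **Primary result.** ANOVA, repeated-measures ANOVA or logistic regression is named for the group comparison, but none is called unadjusted or primary. The only mention of a primary analysis (Missing data) concerns keeping non-compliers under intention to treat. The only sensitivity analysis stated for these comparisons sets complete cases against last observation carried forward.

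**The concern.** Randomisation already protects the arm comparison from systematic confounding. A variable measured months later cannot confound it; it can only differ by chance or because of treatment. A significance trigger therefore selects for adjustment the variables that treatment is most likely to have changed.

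Hypothesis 2 asks whether supplementation improves infant outcomes, which is naturally read as the total effect. Two kinds of damage are possible:

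- If the supplement lowers postpartum stress and stress acts on the infant outcome, adjustment removes that part of the benefit and costs power.
- If mood and outcome merely share unmeasured causes, adjusting for mood that treatment has shifted can create an arm difference where none exists.

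Both need an effect of the supplement on postpartum mood and an association of mood with the outcome. The plan expects the second, since its conceptual model (Innovation) has the postpartum environment continuing to influence brain development. It does not state the first.

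**Working it through.** **1. The plan's own figures.** The plan gives "80% power to detect a difference in the ICQ of 3.7 between the two groups at a given visit", with SD 7.8 and 108 against 54 women.

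- Standard error = 7.8 × √(1/108 + 1/54) = 7.8 × 0.1667 = 1.30.
- Power = Φ(3.7/1.30 − 1.96) = Φ(0.886) = 81% (80.8% with the noncentral t).
- The infant-cortisol statement, "there will be 80% power to detect a difference of 0.19" µg/dL with SD 0.4, also gives 81%.

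Both figures reproduce, and both describe an unadjusted comparison.

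**2. Inputs for the rule.**

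- True effect: 3.7/7.8 = 0.474 SD.
- d: improvement in postpartum mood caused by the supplement, in SDs (assumed).
- r: within-arm correlation of mood with the infant outcome (assumed, 0.1 to 0.5).
- Trigger: two-sided 0.05 (assumed, as the plan says only that the difference is significant).
- Illustrative upper case: the pilot's 30-week perceived stress, "27.5+/-3.4 vs. 29.3+/-3.1". With pooled SD 3.30, d = (29.3 − 27.5)/3.30 = 0.545. This is not a bound.

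**3. Mechanism.** One mood test has noncentrality d/0.1667 = 6d, so the trigger rate rises quickly with d. When adjustment occurs, the expected estimate is 0.474 − r·d. At d = 0.3, r = 0.3 that is 0.474 − 0.09 = 0.384. Averaged over adjusted and unadjusted trials, the simulation gives 0.416.

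**4. Results.** 40,000 simulated trials per cell, one covariate, one visit. Entries separated by slashes are for r = 0.1/0.3/0.5; ranges run over the same values of r. Type I error is for a true null in which mood and outcome share causes only.

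| d | Adjusts | Mean estimate (SD) | Power | Type I error |
|---|---|---|---|---|
| 0 | 5% | 0.47 | 81-82% | 4-6% |
| 0.1 | 9% | 0.46-0.47 | 79-80% | 4-6% |
| 0.2 | 22% | 0.465/0.446/0.428 | 75-79% | 4-6% |
| 0.3 | 43% | 0.454/0.416/0.376 | 76/71/66% | 5-10% |
| 0.545 | 90% | 0.423/0.317/0.213 | 69/48/29% | 6/16/40% |

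In ICQ points, against a true 3.7:

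- d = 0.3, r = 0.3: 0.416 × 7.8 = 3.2.
- d = 0.545, r = 0.3: 0.317 × 7.8 = 2.5.
- d = 0.545, r = 0.5: 0.213 × 7.8 = 1.7.

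Under the null the adjusted estimate centres on 0 − r·d, so the spurious difference runs against the supplement.

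**5. All three mood variables.** 20,000 trials per cell, assumed intercorrelation 0.5, depression d = 0.

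- No carry-over: at least one variable triggers in 12-13% of trials, with no bias.
- Stress and anxiety both at d = 0.3: 62% trigger. The estimate is 0.44-0.33 with power 74-56% if only the significant variables enter, or 0.45-0.35 with power 75-66% if all three do.
- Stress alone at d = 0.3: 48% trigger. The estimate is 0.46-0.38 with power 77-68%, or 0.46-0.41 with power 76-78%, in the same order.

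**6. Alternative.** An unadjusted primary comparison keeps about 81% power and 5% type I error in every cell. A baseline covariate correlated 0.3 or 0.5 with the outcome (assumed) reduces the SD by √(1 − ρ²) and gives 84% or 90%.

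**The case against.** **Carry-over is not shown.** Supplementation stops at delivery. In the pilot, depression was unrelated to supplementation, no stress measure differed at 24 weeks, and perceived stress differed at one prenatal visit only, in a model controlling for life events and depression. The figure 0.545 is also imprecise. Counting all 64 women, SE = √(1/43 + 1/21 + 0.545²/128) = 0.27 and the 95% interval is about 0.01 to 1.07. The reported 47 error degrees of freedom, with four fitted terms, imply about 51 women. An assumed 34/17 split then gives about −0.05 to 1.14. Anxiety is not among the questionnaires listed for the pilot, so its d is purely assumed. All this stands, and it is why 0.545 is only an illustration.

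**The main cortisol test may be untouched.** In a within-visit repeated-measures ANOVA, a mood score that is constant within the visit and entered as a main effect drops out of the group-by-time interaction. This also stands, provided no covariate-by-time term is fitted. It does not protect area-under-the-curve or peak comparisons, or between-arm comparisons of the ICQ, NBAS and Bayley. The figures above describe those single-visit contrasts, and r for cortisol need not equal r for mother-reported temperament.

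**The estimand is undefined, and mothers rate temperament.** If mood colours her ratings, the unadjusted ICQ difference partly reflects reporting. That is a fair reason for a secondary mood-adjusted analysis, but not for letting a significance test choose the main one.

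**The unadjusted result might be kept anyway.** The group test is described first and the factors are said to be controlled for in addition. But nothing says that the first result is retained or takes precedence.

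**Conclusion.** The concern holds. As written, the rule can replace the randomised comparison with one conditioned on a variable that treatment may have changed, and it does so most often when treatment has changed it.

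The size depends on two quantities that the documents do not give. With no carry-over there is no bias, and the rule gains at most about one point of power. Up to d = 0.2 the loss is small: power is at worst 75% and type I error at most 6%. From about d = 0.3 it is material, with power of 66-76% against a planned 80%. The extreme figures (power 29%, type I error 40%) need both full carry-over of the pilot difference and r = 0.5.

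The uncertain reach is a second defect. Only on the wider reading would birth weight, gestation and Apgar be adjusted for mood measured after them. The point should be fixed; confidence in its practical size is moderate.

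**What to change.** - Delete the significance-test trigger for mothers' postpartum stress, depression and anxiety.
- Make the primary Hypothesis 2 comparison unadjusted, or adjusted only for prespecified covariates that are measured at baseline or cannot be affected by treatment (for example baseline perceived stress, infant sex, saliva collection time). State which outcomes each covariate applies to.
- Do not adjust birth weight, gestation or Apgar for postpartum mood.
- Report postpartum-mood-adjusted models only as labelled secondary analyses. The Hypothesis 3 model already lists these variables as possible covariates.

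The cost is wording only. The plan is dated October 2014, a year before the planned October 2015 recruitment start, and no new data are needed: all prenatal visits, including baseline, already collect the stress, depression and anxiety questionnaires (Methods).
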